| | Ta | ble 4: Power for detecting differences in T-cell magnitude. | 17 |
| | Ta | ble 5: Power for detecting differences in T-cell breadth between arms | 188 |
| 6 | Pri | mary Outcome: Safety | 19 |
| | 6.1 | Objective | 19 |
| | 6.2 | Endpoint Analysis | 19 |
| 7 | Sec | condar Outcome: Safety | 20 |
| | 7.1 | Objective | 20 |
| | 7.2 | Endpoint Analysis | 20 |
| 8 | Sec | condary/Exploratory Outcomes: Immunological and Virologic Analysis | 21 |
| | 8.1 | Objectives | 21 |
| | 8.2 | Endpoint Analysis | 23 |
| | 8.3 | Endpoint Analysis Details | 23 |
| 9 | Inte | erim Analyses | 27 |
| 1(| 0 EL | JSPOT Data | 28 |
| | 10.1 | UNC ELISpot assays | 28 |
| | 10.2 | Lab QC Controls | 29 |
| | 10.3 | Reporting | 29 |
| 1 | 1 I | References | 30 |

1 Introduction

This statistical analysis plan (SAP) details the statistical procedures that address the study objectives specified in Protocol version 3.0 of the A Phase I Study to Evaluate the Safety and Immunogenicity of the ChAdOx1.HIVconsv62 - MVA.tHIVconsv4 (C62-M4) or, ChAdOx1.tHIVconsv1+C62 - MVA.tHIVconsv3+M4 (C1C62-M3M4) Prime-Boost Regimens in Persons with HIV-1 Suppressed on Antiretroviral Therapy – The CM (HIV-CORE 008) Study. New versions of the SAP will be issued to document updates and changes in the plan. Any meaningful changes or additions to this SAP (e.g., in response to protocol amendments or violations of assumptions underlying pre-planned analyses), and the timing of such changes, will be documented in in the Revision History.

A DSMB will not be used for monitoring IGHID 12107. Instead, a study monitoring committee (SMC) will convene at least annually to monitor progress and participant safety, and safety data will be communicated to all SMC members on a monthly basis. This will include periodic assessments of recruitments, accrual, retention, and data quality, as well as a recommendation to the Principle Investigator (PI) concerning modifications of the trial based on the observed beneficial or adverse effects of the intervention. The responsibilities of the Safety Monitoring Committee are further described in the SMC Charter. Note, the SMC are not responsible for formal review of immunologic or virologic data. Review and finalization of these data are the responsibility of the Grant PI working with protocol biostatisticians.

1.1.1 Acronyms

| AE | adverse event |
|------|------------------------------------|
| AESI | adverse event of special interest |
| ARV | antiretroviral |
| cART | combination antiretroviral therapy |
| CFAR | Center for AIDS Research |
| C1 | ChAdOx1.tHIVconsv1 |
| C62 | ChAdOx1.HIVconsv62 |
| CI | confidence interval |
| CRF | case report form |
| DSMB | data and safety monitoring board |
| ECRF | electronic case report form |

| HIV | human immunodeficiency virus | | | |
|--------|---|--|--|--|
| IGHID | Institute for Global Health and Infectious Diseases | | | |
| ITT | intention to treat | | | |
| MedDRA | Medical Dictionary for Regulatory Activities | | | |
| M3 | MVA.tHIVconsv3 | | | |
| M4 | MVA.tHIVconsv4 | | | |
| PI | principal investigator | | | |
| PBMC | peripheral blood mononuclear cells | | | |
| PT | preferred term | | | |
| QC | quality control | | | |
| REDCap | Research Electronic Data Capture | | | |
| RNA | ribonucleic acid | | | |
| SAE | serious adverse event | | | |
| SAP | statistical analysis plan | | | |
| SCA | single copy assay | | | |
| SD | standard deviation | | | |
| SFU | spot forming units | | | |
| SIDs | study-specific identification numbers | | | |
| SMC | study monitoring committee | | | |
| SOC | system organ class | | | |
| SOE | schedule of events | | | |
| SOP | standard operating procedure | | | |
| UNC | University of North Carolina | | | |

2 Study Objectives and Summary

Title: IGHID 12107 - A Phase I Study to Evaluate the Safety and Immunogenicity of the

ChAdOx1.HIVconsv62 - MVA.tHIVconsv4 (C62-M4) or, ChAdOx1.tHIVconsv1+C62 - MVA.tHIVconsv3+M4 (C1C62-M3M4) Prime-Boost Regimens in Persons with HIV-1 Suppressed on Antiretroviral Therapy – The CM (HIV-CORE 008) Study

Study Description:

Phase 1, double blind, randomized, placebo-controlled, parallel design study to evaluate the safety and immunogenicity of vaccines **C62** followed by **M4** or **C62** and **C1** together (**C1C62**) followed by **M4** and **M3** together (**M3M4**). Serial

vaccination will be denoted as C62-M4 or C1C62-M3M4.

Hypotheses: Intramuscular (IM) vaccination with C62-M4 or C1C62-M3M4 in persons with

HIV-1 (PWH) on suppressive antiretroviral therapy (ART) will be safe and increase HIV-1-specific T cell responses targeting conserved regions of HIV-1.

Administration of C1C62-M3M4 will result in a greater increase in the breadth of

HIV-1-specific T cells targeting conserved regions of HIV-1 than C62-M4.

Objectives: Primary Objective:

Evaluate the safety of vaccination with i) C62-M4 and ii) C1C62-M3M4 in PWH

on ART through 28 days after the last vaccination or placebo.

Secondary Objectives:

1. Evaluate the safety of vaccination through the end of study

2. Compare the within-participant relative change in magnitude of HIV-1-specific T cell responses following vaccination with **C62-M4** or **C1C62-M3M4**.

3. Compare the between-arm change in breadth of HIV-1-specific T cell responses following vaccination **C62-M4** or **C1C62-M3M4**.

Study Population: PWH, inclusive of men and women \geq 18 and \leq 70 years of age and all ethnicities, with viral suppression on ART and a CD4 cell count \geq 350 cells/mm³ at screening.

Phase: Phase 1

3 Immunogenicity Overview

3.1 Hypothesis

[figure not shown]
Hypothesis 1: Intramuscular (IM) immunization with **C62, C1, M3, M4** vaccines, given individually or in combination (**C62-M4, C1C62-M3M4**) in adult HIV-infected participants on suppressive combination antiretroviral therapy (ART) will be safe and increase HIV-1-specific T cell responses targeting conserved regions of HIV-1.

Hypothesis 2: The simultaneous administration of **vaccines** (**C1C62-M3M4**) will result in a greater increase in the breadth of HIV-1-specific T cells targeting conserved regions of HIV-1 than with the individual administration of **C62-M4**.

3.2 Approach to Immune Testing

The **Mos-1** and **Mos-2** vaccine immunogens differ by 10% at the amino acid levels. This means that T cells targeting identical regions between **Mos-1** and **Mos-2** are the 'same' population of T cells. We therefore do not then 'sum' **Mos-1**- and **Mos-2** specific T cell responses for analysis of any of the vaccine arms. Analyses of **Mos-1**- and **Mos-2**-specific T cell responses are separate.

Figure 1: Mos-1 and Mos-2 immunogens differ by ~ 10% of amino acids. Peptide pools (ppXXX) are indicated in either black (spanning whole immunogen) or teal text (subpools, spanning both immunogens).

Participants will be tested in ex vivo IFN-gamma ELISpot at available visits against peptides spanning the i) Mos-1/PP062 immunogen ii) Mos-2/PP063 immunogen iii) all peptides spanning the Mos-1 and Mos-2 immunogens divided into 5 subpools , PP076-PP080 iv) Clade B HIV Env/PP004 v) Clade B Nef and HIV accessory proteins/PP081 and vi) non-HIV junctions that connect the 6 sections across the M3 and M4 immunogens /PP082B (Table 1 / Figure 1).

Table 1: PPL021 – Peptide Pools tested in CM Study

| Stimulant | Peptide Pool | Descriptor | [final assay] | No. Replicates | Reason for testing | Analysis |
|-----------|--------------|------------------------|---------------|----------------|---|----------|
| Mock | 1 | Culture media- only | 1 | | Negative control to assess non-specific IFN-g production | AII |

| M3 | PP062 | 18mer peptides (119) overlapping by 11aa spanning Mosaic-1 immunogen | 2ug/ml | 4 | Spans 6 highly conserved regions of HIV, all from Gag and Pol. Based on a M clade. We will examine if vaccination increases/induces responses to these conserved HIV regions. We expect that in placebo group that T cell responses will be stable. | Secondary: Magnitude (SFU/10^6 PBMC) |
|-----------------------------|-------|---|--------|---|--|---|
| M4 | PP063 | 18mer peptides overlapping (119) by 11aa spanning Mosaic-1 immunogen | 2ug/ml | 4 | Spans 6 highly conserved regions of HIV, all from Gag and Pol. Based on a M clade. Mos-1 differs from Mos-2 at about 10% of aa We will examine if vaccination increases/induces responses to these conserved HIV regions. We expect that in placebo group that T cell responses will be stable. | Secondary: Magnitude (SFU/10^6 PBMC) |
| G1 (MOS1+MO S2) | PP076 | 18mer peptides overlapping (64) by 11aa spanning G1 of both Mosaic-1 and Mosaic-2 | 2ug/ml | 4 | Examining breadth at the subpool level. Also, a second an independent check of Mos-1/Mos-2 data. Specifically, we expect any changes in Mos-1- or Mos-2-specific T cell responses to be reflected in changes at the sub-pool level. | Secondary: Breadth (0-5) |
| G2_P4 P5 (MOS1+MO S2) | PP077 | 18mer peptides overlapping (38) by 11aa spanning G2, P4 and P5 of both Mosaic-1 and Mosaic-2 | 2ug/ml | 4 | Examining breadth at the subpool level. Also, a second an independent check of Mos-1/Mos-2 data. | Secondary: Breadth (0-5) |
| P3-A (MOS1+MO S2) | PP078 | 18mer peptides overlapping (42) by 11aa spanning the 5` half of P3 of both Mosaic-1 and Mosaci-2 | 2ug/ml | 4 | Examining breadth at the subpool level. Also, a second an independent check of Mos-1/Mos-2 data. | Secondary: Breadth (0-5) |

| P3-B (MOS1+MO S2) | PP079 | 18mer peptides overlapping (54) by 11aa spanning the 5` half of P3 of both Mosaic-1 and Mosaic-2 | 2ug/ml | 4 | Examining breadth at the subpool level. Also, a second an independent check of Mos-1/Mos-2 data. | Secondary: Breadth (0-5) |
|-------------------------|----------------|--|--------|---|--|--|
| P6 (MOS1+MO S2) | PP080 | 18mer peptides overlapping (41) by 11aa spanning the 5` half of P3 of both Mosaic-1 and Mosaic-2 | 2ug/ml | 4 | Examining breadth at the subpool level. Also, a second an independent check of Mos-1/Mos-2 data. | Secondary: Breadth (0-5) |
| Clade B Env | PP004 | Overlapping 18mer peptides spanning Clade B Envelope (year) | 2ug/ml | 4 | Not in vaccines. i) Descriptive analysis of whether vaccination has any nonspecific effects on ENV-specific T cell responses in ELISpot ii) Immunodominance analysis | Exploratory: (SFU/10^6 PBMC) |
| Clade B Nef/Acc | PP081 | Overlapping peptides spanning Nef, Rev, Tat, Vif, Vpr, Vpu | 2ug/ml | 4 | Not in vaccines. i) Descriptive analysis of whether vaccination has any nonspecific effects on ENV-specific T cell responses in ELISpot ii) Immunodominance analysis | Exploratory: (SFU/10^6 PBMC) |
| Junctions | PP082 B | Overlapping peptides spanning junctional sequences between the 6 HIV regions of the vaccine immunogens across the four immunogens inC1, C62, M3,M4 | 2ug/ml | 4 | In the vaccine immunogen, but not HIV-specific. Descriptive analysis as to whether vaccination induced T cell response to these regions | Exploratory: (SFU/10^6 PBMC) |
| РНА | 1 | Phytohemagglutini n (mitogen) | 5ug/ml | 2 | Positive control to confirm T cell functionality | Lab QC Control, data not submitted |

4 Statistical Methods

4.1 General Analytic Considerations

4.1.1 Study Duration and Accrual

Participants will be screened approximately 60 days prior to vaccination and will be followed for 196 days after vaccination. The total study duration from screening to completion of follow-up per participant will be approximately 36 weeks (9 months). Given the focus of this study is on safety and potential adverse events, accrual will be staggered such that enrollment and treatment administration will include a maximum of 2 participants per week.

4.1.2 Randomization

Following enrollment, the 18 study participants will be randomly assigned to receive one vaccination with either C62-M4 (n=8), C1C62-M3M4 (n=8) or placebo (n=2) through a double-blind, placebo-controlled, block randomization design. This design has been chosen to minimize bias in the reporting of safety and immunological data. When the participant's eligibility is confirmed, the study-specific identification numbers (SIDs) will be assigned sequentially as each participant enrolls at the study. The arm assigned to the participant at randomization is summarized in Table 2.

Table 2: Randomized assignment

| Arm | N | D a y | Treatment | Total Dose (vp) | Route | Day | Treatment | Total Dose (pfu) | Route |
|-----|---|-------------|-----------|-----------------------|-------|-----|----------------------|------------------------|-------|
| 1 | 8 | 0 | C62 | 5×10 ¹⁰ | IM | 28 | M4 | 1.8×10 ⁸ | IM |
| 2 | 8 | 0 | C1C62* | 5×10 ¹⁰ | IM | 28 | M3M4 [#] | 1.9×10 ⁸ | IM |
| 3 | 2 | 0 | Placebo◊ | - | IM | 28 | Placebo [◊] | - | IM |

C6= ChAdOx1.HIVconsv62 (mosaic 2)

C1 = ChAdOx1.tHIVconsv1 (mosaic 1)

M4 = MVA.tHIVconsv4 (mosaic 2)

M3 = MVA.tHIVconsv3 (mosaic 1)vp = virus particles

pfu = plaque forming units

IM = intramuscular

* 2.5×10^{10} vp, each vaccine

#0.9×108 pfu M4; 1.0×108 pfu M3

[◊] normal saline

4.1.3 Blinding

Vaccine and placebo product will be indistinguishable. Site, laboratory personnel, and study participants will be blinded with respect to the allocation of vaccine or placebo. The randomization plan will be generated centrally by the study statisticians at the UNC CFAR using computer software and will be kept concealed from the study personnel. The study personnel will be made aware that the randomization will take place in blocks, but will be naïve to the block size used for randomization. As such, the specific block size is not addressed in this document.

4.1.4 Unblinding

Un-blinding of an individual participant is indicated in the event of a medical emergency where the clinical management would be altered by knowledge of the group assignment. The decision to unblind will be taken in conjunction with the independent members of the SMC. Procedures and contact details for un-blinding procedures will be held in a site-specific SOP. The site study personnel will ensure that the reasons for un-blinding are documented in the CRF.

Study un-blinding of the research team can occur 28 days after the last participant receives their vaccine/placebo booster injection and following completion of an independent SMC review. Unblinding of study participants can commence days after all participants have completed the last study visit and all queries and outstanding protocol implementation requirements have been resolved.

4.1.5 Data Sources

The Data Management Plan is detailed in a separate, protocol-specific document. The Advarra Electronic Data Capture (EDC) clinical research management tool will be utilized as the clinical database for the IGHID 12107 clinical trial. Study Staff will be trained to enter all study-captured events and AE information in the appropriate electronic case report forms (eCRFs). QC reports from the data manager will be used to manage and resolve data inconsistencies, and AEs will be coded per the Medical Dictionary for Regulatory Activities (MedDRA). Upon completion of the interim and final databases, the statistician will be responsible for independent review before finalization of the database.

4.1.6 Baseline Data

Baseline demographic data, medication history, and laboratory data will be summarized using descriptive statistics (e.g. frequencies, percentages, means, medians, interquartile ranges, minima, and maxima). When continuous data has clinically meaningful cut-points (e.g. age distribution, laboratory data), the data may be summarized into categories for easy interpretation, providing that the analyses are not affected by this categorization. Summaries will be provided for the screened cohort and by randomized arms and placebo.

4.1.7 Missing Data

Based on previous experience with similar trials, we anticipate that the amount of missing or invalid data will be small. All participants who are evaluable for adverse event assessment will be included in the safety analyses, regardless of whether they are replaced or missing for additional endpoints. Participants who do not start study treatment or are unable to provide the first or second leukapheresis will be replaced to achieve the planned evaluable sample size. Given the small size of this study, formal imputation methods will not be used. To assess whether key findings are sensitive to missing data, missing values can be replaced with worst possible outcomes as a sensitivity analysis (e.g., by replacing missing values in the C62-M4 only arms with the best rank and replacing missing values in the C1C62-M3M4 arm with the worst rank, to assess if a finding regarding the C62-M4 arm is sensitive to missing data).

4.1.8 Test Size and Confidence Levels

For all primary and secondary endpoints in this trial, 95% confidence intervals will be computed for all relevant estimates. Because this is a Phase I study with a small sample size and exploratory endpoints, results will be presented without adjustment for multiple comparisons or multiple testing of endpoints. Given the small sample size, exact methods that do not rely on large sample assumptions will be used for statistical inference and will always be presented with corresponding descriptive statistics and/or data visualization. Type-I error control (alpha) for all comparisons will be set to 0.05, and all tests will be two-sided.

4.2 Visit Schedule and Analysis Windows

Per protocol,

- 1) Perform visits per window list in the SoA, Section 1.3 of the protocol. There is no window around the Day 2, Day 7, Day 30, and Day35 visits. There is a ±2 days window around the visits at Days 14, 28, 42, and 56.
- 2) There is a ±1 day window around the telephone call assessments at Days 5, 10, 18, and 22.
- 3) There is a \pm 7 days window around the visits at Days 84 and 140. D196 has a \pm 14 days window.
- 4) Post D28 visits are scheduled based on the date of D28 booster vaccination. Consequently, D30 will occur exactly 2 days after booster vaccination, D35 will occur exactly 7 days after, D42 will occur 14 days (+/- 2 days) after, and so on.

Window for D56 leukapheresis is -7/+21 days with preference for the procedure to be completed as close to Day 56 as possible. If unable to complete the D56 leukapheresis and upon review and approval of the protocol PI, a large blood draw can be completed between 14-21 days after D56 (Days 70-77). This large blood draw will be completed as close to 21 days after D56 as possible (Section 8.2.3)

All measures on or before the randomization date are grouped and averaged. Analysis visit windows will be constructed around each study visit using the target windows given in Table 3. If there are multiple evaluations within the window for a given visit, the evaluation closest to the scheduled study day will be used.

Table 3: Target visit windows

| Visit | Visit Type | Lower Target Window (-) | Target Day | Upper Target Window (+) |
|-------|-----------------------|----------------------------|------------|----------------------------|
| 1.0 | Screening | N/A | -60 | N/A |
| 2.0 | Enrollment & Baseline | -60 | -10 | 0 |

| | Enrollment | After -60 | -10 | 0 |
|------|------------------------|-----------|-----|-----|
| | | Aiter -00 | -10 | O |
| | leukapheresis | | | |
| 3.0 | Day 0 | -10 | 0 | 0 |
| 4.0 | Day 2 | N/A | 2 | N/A |
| 5.0 | Day 7 | N/A | 7 | N/A |
| 6.0 | Day 14 | 12 | 14 | 16 |
| 7.0 | Day 28 | 26 | 28 | 30 |
| 8.0 | Day 30 | N/A | 30 | N/A |
| 9.0 | Day 35 | N/A | 35 | N/A |
| 10.0 | Day 42 | 40 | 42 | 44 |
| 11.0 | Day 56 | 54 | 56 | 58 |
| | Day 56 leukapheresis * | 49 | 56 | 77 |
| 12.0 | Day 84 | 77 | 84 | 91 |
| 13.0 | Day 140 | 133 | 140 | 147 |
| 14.0 | Day 196 | 182 | 196 | 210 |

^{*}If no post-vaccination leukapheresis is performed (e.g. poor venous access) then a large blood draw will be collected within 21 days of Visit 11.

5 Study Size and Power

5.1 Primary Sample Size Determination

From previous publications employing ChAdOx1- and MVA- vectored vaccines, the proposed number of participants (8 vaccinees per arm and 2 placebo controls) is sufficient to evaluate the risk of SAEs or severe local or systemic reactions in the study population. Descriptive analyses will be used to summarize adverse or SAEs in each arm.

5.2 Upper Confidence Limits for Primary Safety Endpoint

The trial will be suspended if two participants experience a study treatment-related toxicity of Grade 3 or higher as defined in the primary safety endpoint. Safety events of grade three or higher will be estimated with an exact binomial 95% 1-sided upper confidence limit. If zero of 8 participants experience a safety event, a 95% 1-sided exact binomial upper confidence limit for the probability of

a safety event will be 31%. If one participant experiences a safety event, the corresponding 95% 1-sided upper confidence limit will be 47%. If zero safety events are observed in the two vaccine arms and data are pooled across arms (n=16), then the upper limit of the exact, 1-sided 95% confidence interval (CI) will be 17%.

5.3 Power Calculations for Secondary Endpoints

Table 4 and Table 5 provide power calculations for both immunogenicity secondary endpoints. For the first of the secondary endpoints, the outcome will be the HIV-specific T cell response to peptides spanning either the Mos-1 (PP062) or Mos-2 (PP063) immunogens at baseline visits, Day 35, and Day 42 (following C62-M4 or C1C62-M3M4 vaccination). For the within arm calculation, an average fold change of at least 2 (comparing T-cell responses within participants) is anticipated to be scientifically meaningful. For the between arm calculation, a relative change that is greater for any given participant in the C1C62-M3M4 arm than in the C62-M4 arms alone is anticipated to be scientifically meaningful if it occurs at least 90% of the time.

For the second of the secondary endpoints, the outcome will be breadth of T-cells targeting peptide subpools (n=5 subpools PP076, PP077, PP078, PP079, PP080) spanning the conserved immunogens of HIV-1. HIV-specific T-cell responses will be measured at pre-vaccination visits (1-3 visits/participant) and at post-vaccination (Day 56).

Table 4: Power for detecting differences in T-cell magnitude.

| Within Arms | Between Arms (C1C62-M3M4 vs C62-M4) |
|--|---|
| Aim: Determine the statistical power necessary to detect a geometric mean ratio (GMR) of 2 for the within-participant HIV-specific T-cell response. | Aim: Assuming identical distributions of differences in both arms (i.e. assuming a location-shift-only alternative), determine the statistical power necessary to compare median differences in HIV-specific T-cell responses. |
| Data: Assume normally distributed natural, log-transformed, HIV-specific T cell responses from | Data: Assume normally distributed differences in HIV specific T-cell response |

pre-vaccination (one or more of screening, enrolment, pre-vaccination leuk, Day 0) and postvaccination (Day 35 and 42) for all arms. between pre-vaccination (screening, enrolment, pre-vaccination leuk, Day 0) and post-vaccination (Day 35 and 42) for vaccine arms.

Design: Empirical power calculated by simulating 10,000 random samples, assuming log-transformed HIV-specific T-cell response follows a normal distribution. The effect under the alternative hypothesis was a GMR of 2 on the raw T-cell response measures. An SD of 0.8 for both pre- and post-vaccination measurements was assumed to calculate power. This assumption was based on previous, log-transformed HIV-specific T-cell response data, which gave a between-participant SD of 0.8 at baseline. A within-participant Pearson correlation of between r = 0.8 and r = 0.9 was assumed between paired log-transformed HIV-specific T-cell response measures.

Design: Empirical power calculated by simulating 10,000 random samples from a normal distribution. Assume a p=90% or p=87% probability that the difference in HIV-specific T-cell response for any given participant in the **C1C62-M3M4** arm is higher than any given individual in the **C62-M4** arm.

Statistical Test for Power: Two-Sided Exact Wilcoxon Signed-Rank Test to achieve exact p-value < 0.05

Statistical Test for Power: Two-Sided Exact Wilcoxon Rank-Sum Test to achieve exact p-value < 0.05

| Sample Size: N=8 (per arm) | Sample Size: N=8 (per arm) |
|----------------------------------|----------------------------|
| Empirical Power: | Empirical Power: |
| >95% (within-individual r = 0.9) | 90% (p=90% effect size) |
| >80% (within-individual r = 0.8) | >80% (p=87% effect size) |

Table 5: Power for detecting differences in T-cell breadth between arms.

Aim: Determine the statistical power necessary to detect a change in T-cell breadth (T cell breadth is defined as the number of reactive HIV subpools as described in Section 8.2) between vaccine arms

Data: For the C62-M4 and C1C62-M3M4 arms, we anticipate that vaccination will induce a change of breadth (the detection of a new reactive T cell epitope) ranging from 0-3 epitopes and 2-6 epitopes, respectively. We anticipate that C62-M4 will induce a change in breadth with the following frequency distribution: 0 (20% of participants), 1 (50%), 2 (20%), and 3 (10%). We anticipate that C1C62-M3M4 will induce a change in breadth with the following frequency distribution: 2 (30% of participants), 3 (40%), 4 (15%), 5 (10%), and 6 (5%). Note, that these estimates are based on previous empirical

mapping of HIV-specific T cells against 'individual' peptides spanning Gag/Pol regions corresponding to the HIVconsvX immunogens [1]. In the breadth analysis here, we first examine change of breadth to subpools (n=5) of peptides spanning the HIVconsvX immunogens. Future exploratory analyses will examine change in breadth at the individual peptide level.

Design: Calculate empirical power by simulating 10,000 random samples (as described in Data) from the **C1C62-M3M4** cohort. Compare this generated sample to **C62-M4** only, assuming zero change in T-cell breadth. Count the number of successes (p-values < 0.05).

Statistical Test for Power: Two-Sided Exact Wilcoxon Rank-Sum Test to achieve exact p-value < 0.05

Sample Size: N=8 (per arm)

Empirical Power: 95%

6 Primary Outcome: Safety

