10.7.4.4 Power Calculations for T cell Breath

Baseline HIV-specific T cell breadth from durably-suppressed PWH were used to inform power calculations (50). In this study, reactive HIV T cell epitopes in the HIV proteome (Clade B consensus and autologous reservoir virus) were defined in 25 PWH on ART.

For the **C62-M4** and **C1C62-M3M4** arms, we anticipate that vaccination will induce a change of breadth (the detection of a new reactive T cell epitope) ranging from 0-3 epitopes and 2-6 epitopes, respectively.

- We anticipate that **C62-M4** will induce a change in breadth with the following frequency distribution: 0 (20% of participants), 1 (50%), 2 (20%), and 3 (10%).
- We anticipate that **C1C62-M3M4** will induce a change in breadth with the following frequency distribution: 2 (30% of participants), 3 (40%), 4 (15%), 5 (10%), and 6 (5%).

Given these assumptions, n=8 evaluable participants per treatment arm provides 95% power to detect a difference between arms using an exact two-sided Wilcoxon rank-sum test (at a 0.05 significance level).

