relative change within participants will be estimated using a geometric mean ratio (GMR, also known as fold change) and evaluated with an exact two-sided Wilcoxon signed-rank test for within-arm comparisons and an exact two-sided Wilcoxon rank-sum test for between-arm comparisons. The Wilcoxon signed-rank test assumes symmetry of the change in natural log-transformed summed HIV-1 specific T cell response (estimated by GMR) under the null. If this assumption is violated, then a sign test will be conducted as a sensitivity analysis.

Outcome 2 (T-Cell Breadth): Change in breadth (difference in the number of ex vivo reactive/positive P076, PP077, PP078, PP079, PP080 subpools pre- and post-vaccination) of T-cell responses targeting HIV-conserved regions from pre-vaccination (one or more of screening, enrolment, pre-vaccination leuk, Day 0) to post-vaccination (Day 56).

This outcome consists of the following two components:

Outcome 2.1: Change in breadth of T-cell responses from pre-vaccination to post-vaccination (Day 56) within vaccinated arm.

Outcome 2.2: Comparison of change in breadth of T-cell responses from pre-vaccination to post-vaccination (Day 56) between vaccinated arms.

Analysis: Breadth is measured as the number of ex vivo reactive subpools (P076, PP077, PP078, PP079, PP080). To evaluate change in breadth in the number of T cell responses targeting HIV-conserved regions from baseline (pre-vaccination) to post-vaccination (D56), an exact two-sided Wilcoxon signed-rank test will be used for within-arm comparisons and an exact two-sided Wilcoxon rank-sum test will be used for between-arm comparisons.

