 - i. Report results as log2 fold change to each antigen pool (Mos-1/PP062, Mos-2/PP063, Subpools PP076-080) for each vaccine arm.
 - ii. All log2 fold changes will be statistically assessed using a two-sided exact Wilcoxon signed-rank test. If a value in the dataset matches the hypothetical value, then the value will be ignored in the analysis (Wilcoxon method of handling ties).
 - c. Secondary analyses between vaccine arms (n=8/group):
 - i. Examine the between-arm difference in log2 fold change to each antigen pool Mos-1/PP062 and Mos-2/PP063 pre- and post-vaccination.
 - ii. Between-arm comparisons in log2 fold changes will be statistically assessed using a two-sided exact Wilcoxon rank-sum test. If a value in the

dataset matches the hypothetical value, then the value will be ignored in the analysis (Wilcoxon method of handling ties).

C. Calculate gain or loss of a positive T cell responses to vaccine immunogens to assess breadth (Outcome 2 T-Cell Breadth):

- a. To analyze breadth, we are looking at the number of reactive subpools before (screening, enrollment, Day 0) and after vaccination (Day 56).
- b. As per section 8.3.A.b, assess whether ex vivo T cell response is reactive/positive at each visit.

c. Analysis criteria:

- i. For breadth analysis, output should be binary: non-response or response
- ii. No. of positive HIV subpools 1-5 (PP076-PP080) pre-vaccination at baseline.
- iii. Pre-vaccination breadth: if a reactive/positive T cell response is observed at *any* pre-vaccination visit that the participant will be deemed to have a positive/reactive T cell response pre-vaccination.
- iv. No. of positive antigen subpools 1-5 (PP076-PP080) post-vaccination.
 - Post vaccination breadth: ex vivo vaccine-induced T cell response must be detected at > 1 post-vaccination visit, Day 35 onward.
- v. Data was only submitted for analysis if it met biological criteria.
- d. Secondary analysis across all vaccinees (n=16) & within arm (n=8/group):
 - i. Change in number of positive HIV subpools (PP076-80) at Day 56 (post-vaccination) vs baseline (pre-vaccination) across all vaccinees (n=16).
 - ii. Change in number of positive/reactive HIV subpools (PP076-80) at Day 56 (post-vaccination) vs baseline (pre-vaccination) for each vaccine arm.
 - iii. The change in number of positive/reactive antigen subpools will be statistically assessed using a two-sided exact Wilcoxon signed-rank test. If

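### The 95% power for T-cell breadth in SAP Table 5 is computed on epitope gains, but the endpoint counts five subpools; the table's Design row as written would give 100%

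*SAP*

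**What the plan says.** **Endpoint.** The Aim row of SAP Table 5 (section 5.3) states that "T cell breadth is defined as the number of reactive HIV subpools". SAP 8.2, Outcome 2, agrees: "Breadth is measured as the number of ex vivo reactive subpools". SAP Table 1 labels each of the five subpools PP076 to PP080 "Secondary: Breadth (0-5").

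**Power inputs.** The Data row of Table 5 gives gains in newly detected epitopes. For C62-M4 these are 0, 1, 2 and 3 with probabilities 20%, 50%, 20% and 10%. For C1C62-M3M4 they are "2 (30% of participants), 3 (40%), 4 (15%), 5 (10%), and 6 (5"%). A note says these come from mapping against individual peptides and adds: "In the breadth analysis here, we first examine change of breadth to subpools (n=5) of peptides spanning the HIVconsvX immunogens". It leaves peptide-level breadth to later exploratory work.

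**Design row.** The C1C62-M3M4 samples are simulated from the Data row and compared with C62-M4, "assuming zero change in T-cell breadth". The test is a two-sided exact rank-sum test at 0.05 with 8 per arm, and the stated power is 95%.

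**Protocol.** Section 10.7.4.4 uses the same two epitope distributions and concludes that "n=8 evaluable participants per treatment arm provides 95% power to detect a difference between arms". It does not contain the zero-change clause.

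**Baseline rule.** SAP 8.3.C begins "Pre-vaccination breadth: if a reactive/positive T cell response is observed at" and goes on to count a response at any pre-vaccination visit as positive at baseline.

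**The concern.** Table 5 uses two units. Its Aim is the subpool count; its inputs are epitope counts. The note discloses the difference but makes no conversion, and the table still attaches 95% to the subpool Aim. Two things shrink gains when epitopes become subpools: several new epitopes can fall in one subpool, and a new epitope can fall in a subpool that was already reactive. The any-visit baseline rule makes the second more likely.

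The Design row raises a separate problem. It gives C62-M4 no change at all, whereas the Data row gives 80% of that arm a gain of at least 1.

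Greater breadth with C1C62-M3M4 than with C62-M4 is a stated hypothesis (Protocol 10.1, SAP 3.1), and this is the power quoted for testing it. A null result could be read as evidence against the bivalent regimen on the strength of a power that was never shown for that endpoint.

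**Working it through.** All simulations use 8 per arm, the exact two-sided permutation rank-sum test with midranks for ties, and rejection at p < 0.05.

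**1. Reproduce the stated figure.** Draw both arms from the Data row. The mean gains are:
- C62-M4: 0(0.20) + 1(0.50) + 2(0.20) + 3(0.10) = 1.2 epitopes.
- C1C62-M3M4: 2(0.30) + 3(0.40) + 4(0.15) + 5(0.10) + 6(0.05) = 3.2 epitopes.

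The difference is 2.0 epitopes. Power is 95.1% in 20,000 simulated trials and 95.7% in a separate run of 10,000. The stated 95% is therefore correct on the epitope scale.

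**2. Design row as written.** All eight C62-M4 values are 0 and all eight C1C62-M3M4 values are at least 2. The arms separate completely in every trial, so p = 2/C(16,8) = 2/12,870 = 0.000155. Power is 100%, not 95%.

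**3. Remove only the impossible value.** Cap gains at 5 with no reactive subpool at baseline: power stays at 95%. The gain of 6 shows that the units differ but does not itself cost power.

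**4. Subpool scale.** The documents give neither a baseline subpool distribution nor an epitope-to-subpool mapping, so each mapping below is an assumption:
- (a) baseline and new epitopes fall independently and at random among five equal subpools;
- (b) each participant's new epitopes fall in different subpools, which may already be reactive at baseline;
- (c) every new epitope opens a previously negative subpool, until all five are reactive.

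Baseline epitopes are placed at random. Power from 6,000 trials per cell, by number of baseline epitopes per participant:

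| Mapping | 0 | 1 | 2 | 3 | 4 |
|---|---|---|---|---|---|
| (a) | 84% | 67% | 47% | 33% | 24% |
| (b) | 96% | 86% | 73% | 57% | 42% |
| (c) | 95% | 96% | 93% | 87% | 60% |

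Under (c) with 3 baseline epitopes in three different subpools, power is 81%. Weighting subpools in (a) by their peptide counts (64, 38, 42, 54, 41, from SAP Table 1) changes little: 31% at 3 baseline epitopes, against 35% with equal weights in the same run.

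**5. Why power falls at 3 baseline epitopes.** Protocol 2.2.3.1 reports an average of 3 targeted epitopes within the immunogen, range 0 to 6. The chance that a given subpool is negative at baseline is (4/5)³ = 0.512. For an epitope gain g, the expected subpool gains are:
- (a) 5 × 0.512 × [1 − (4/5)^g]. Averaged over the Data row this is 0.57 for C62-M4 and 1.27 for C1C62-M3M4, a difference of 0.7.
- (b) 0.512 × min(g, 5). This is 0.512 × 1.2 = 0.61 and 0.512 × 3.15 = 1.61, a difference of 1.0.
- (c) min(g, 5 − B), where B, the number of baseline subpools, is 1, 2 or 3 with probabilities 0.04, 0.48 and 0.48. C62-M4: 0.04(1.2) + 0.48(1.2) + 0.48(1.1) = 1.15. C1C62-M3M4: 0.04(3.0) + 0.48(2.7) + 0.48(2.0) = 2.38. The difference is 1.2.

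The assumed difference of 2.0 epitopes thus becomes 0.7 to 1.2 subpools.

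**The case against.** The strongest reply is that nothing was miscalculated or hidden. The 95% follows from its inputs, the impossible 6 is harmless, and the note beside the figure says that the inputs are peptide-level and the analysis is subpool-level. The zero-change clause may be a misplaced statement of the null hypothesis. Breadth is a secondary endpoint, sample size rests on safety (Protocol 10.3, SAP 5.1), and Protocol 10.7.1 already warns that meaningful effects may be missed. Much of the assay text in SAP 10 is in the past tense, so a new prospective power figure may have limited use.

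Most of this is fair, and it limits the point to Table 5. It does not make the 95% a power for the planned endpoint. Disclosing a different scale is not a conversion, and a general caution does not correct a specific figure. The Design row refers to the Data row only for C1C62-M3M4, so as written the zero change describes the comparator.

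A second objection also has force: the subpool figures are not bounds. They fix the baseline count for every participant. They also equate mapped epitopes with ex vivo positivity and ignore the SAP's positivity thresholds, the requirement of a response at more than one post-vaccination visit, and losses of reactivity. Letting the baseline spread evenly over 0 to 6 epitopes gives roughly 30% under (a), 47% under (b) and 67% under (c), so relaxing the fixed baseline in this way lowers the range.

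**Conclusion.** The concern holds. The 95% is a valid epitope-scale figure, but it matches neither the subpool endpoint that Table 5 names nor the simulation its Design row describes, which gives 100%. At 3 baseline epitopes per participant, every mapping tried falls below 95%, to about 33% to 87%. With few or no baseline responses and a favourable mapping, power can stay near 95%. The documents do not show which case applies, so no single corrected figure can be given. The range rests on the assumed mappings and on taking the cited cohort's average as the baseline. The consequence is for reading a null breadth result; enrolment does not depend on this figure.

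**What to change.** In SAP Table 5:
1. Add power for change in the number of positive subpools (0-5). State and source the baseline subpool distribution, state the epitope-to-subpool assumption, and report a range over plausible mappings.
2. Keep the existing 95% only with a label saying that it is on the epitope scale and does not apply to the planned subpool endpoint.
3. In the Design row for that epitope-scale figure, say that both arms are sampled from the Data-row distributions, and delete the zero-change clause. Describe the subpool simulation separately.

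In Protocol 10.7.4.4, whose 95% is consistent on its own scale, add one sentence saying that the figure refers to epitopes and that the SAP analyses subpools.

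The cost is a short re-simulation, revised table text and one Protocol sentence. The stated power becomes a range that depends on assumptions and is probably lower than 95%. Enrolment, endpoint and test do not change.
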